QC Quality Control

SAE Serious Adverse Event/Serious Adverse Experience

SOP Standard Operating Procedure

SRP Scaling and Root Planing
UP Unanticipated Problem

PROTOCOL SUMMARY

Title:

Shaping the Indications for Periodontal Adjunctive Antibiotics in Dental Practice: A PBRN Clinical Trial (PAAS)

Précis:

Periodontitis is a bacterial inflammatory disease and antibiotic use is being empirically used as part of its treatment. However, a clinical practice guideline on periodontal treatment adjuncts published in 2015 identified weak evidence on the use of systemic antibiotics and large heterogeneity across small scale studies, suggesting that larger pragmatic clinical trials would benefit clinical decision making. This will be a prospective, randomized, placebo-controlled trial, stratified by practice and practitioner. The study will investigate the effectiveness of adjunctive antibiotics as adjunct to scaling and root planing (SRP) compared to SRP with placebo for the treatment of generalized stage II-III, grades A-C periodontitis in approximately 544 patient participants from about 34 National Dental PBRN practices. Periodontal data will be collected at baseline, re-evaluation (6 weeks), and final (12 month) study visits. Changes in periodontal clinical and patient-reported outcomes will be assessed to determine the effectiveness of SRP plus adjunctive systemic Amoxicillin / Metronidazole antibiotics (AMXM) versus SRP with Placebo.

Objectives and Outcomes:

Primary: The primary objective will assess the effectiveness of SRP plus adjunctive antibiotics compared to SRP with placebo in periodontitis individuals from baseline to 6 weeks and 12 months following non-surgical periodontal therapy (NSPT) as determined by changes in site-level periodontal probing depth (PD).

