3 OBJECTIVES AND OUTCOME MEASURES

3.1 Primary

Objective	Brief Description/Justification of Outcome Measure	Outcome Measured By	Time Frame
Assess the effectiveness of SRP plus AMXM compared to SRP with placebo in periodontitis individuals at baseline, reevaluation (6 weeks), and final visit (12 months) following intervention.	The primary outcome of treatment effectiveness will be assessed by full-mouth probing depth (PD) at 6 weeks to 12 months post-intervention adjusted for baseline PD. These are considered universal, standard assessments used to determine periodontal status (Tonetti et al. 2018). A double-blinded patient participant-randomized design is used to assign patient participants to SRP plus AMXM versus SRP plus placebo prior to treatment.	Outcome: Probing Depth (PD) in millimeters. Full- mouth PD measurements (excluding 3rd molars) will be obtained utilizing a UNC 15mm periodontal probe. Level of analysis: site Outcome Type: continuous	Baseline, Re- evaluation (6 weeks), and Final study visit (12 months) after intervention.

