Step 1: Identify periodontal patients who need to receive a minimum of two quadrants of SRP for periodontal treatment.

Step 2: Evaluate medical history (ASA status) and age inclusion requirements.

Step 3: Confirm that the rest of the eligibility criteria are met, via an electronic screening questionnaire, and as per the screening table below.

Patient participant eligibility Criteria

- At least 40 years of age
- ASA Class I or II
- ≥ 20 teeth, excluding third molars
- Needs periodontal care for Generalized stage II-III, Grade A-C periodontitis
- Indicated to receive SRP in a minimum of 2 quadrants with CDT code 4341
- If diabetic, HbA1c is ≤ 10%
- Willing and able to provide informed consent

- Is NOT currently pregnant or breastfeeding
- Does NOT have a known drug allergy to antibiotic or anesthetics
- No systemic antibiotics within the last 3 months
- No medical condition that requires antibiotic prophylaxis prior to receiving dental treatment

Patient participant Retention: We have estimated for 20% attrition at 12 months. Because the primary endpoint occurs 12 months following treatment and because periodontal patients are usually lifetime patients where maintenance visits are an integral part of periodontitis management, we believe the attrition rate is reasonable. To minimize loss to follow-up, we will work with the study management team at the NCC and regional Node staff to increase retention including study visit reminders to practitioners and patient participants.

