12.4 Final Analysis Plan

Analysis Population: All analyses will be intent-to-treat, i.e., all participants who provide data at baseline will retain their original assignment regardless of the treatment received. All statistical tests will be evaluated using a two-tailed alpha level of .05 and will express precision using 95% confidence intervals.

Center Effects: The Primary analysis will account for variation between centers using a mixed effects model. The empirical Bayes estimate of center effects resulting from this model will be analyzed to assess the degree of heterogeneity between centers by assessing the magnitude of the variance of the random effects. This assessment will consist of a formal statistical test to determine if the variance of the random effect is greater than zero as well as an assessment of its estimated magnitude. If a clinically meaningful amount of variability between centers is detected, exploratory analyses will be conducted to attempt to identify covariates related to center effects including

geographic information, demographic information, and disease-related information. If these analyses identify meaningful subgroups among the centers, subgroups of sites will be created based on the potential for differential effectiveness. These subgroup analyses will be considered secondary and will be conducted in a manner identical to the primary analysis provided that the subgroups are of sufficient size to merit such an analysis. The specific data related to the characteristics of these subgroups, should they prove to exist, will be reported separately.

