Primary Outcome Analysis: We will test the primary study hypothesis, which posits the AMXM intervention to be more effective than placebo in reducing periodontal probing depths, using a hierarchical linear model (HLM; aka mixed models, random coefficients regression). This analysis will account for the correlation between longitudinal observations within tooth site, within participants, and by practitioner, each of which can be represented within the model by a random intercept. The primary outcome measure, PD in mm, is effectively continuous, within a fixed range being necessarily positive and bounded above by the anatomy of the tooth in question. The model will include the fixed effect of time by using two dummy indicators representing re-evaluation at 6 weeks and final study visit at 12 months. The model will also include a binary indicator for arm (AMXM vs placebo) and an interaction between the indicators for time and study arm. Significance of either interaction term will represent a difference between the treatment and control arm at that timepoint, with the 6-week time representing efficacy and the 12-month time representing long-term efficacy/durability. No transformation of these variables is likely to be necessary.

It is not presently anticipated that boundary value problems or deviations in the residual distribution of the primary outcome will negatively impact the proposed analysis' operating characteristics due to the large size of the study. However, sensitivity of the analysis to these factors will be assessed using residual plots. In addition, potential site effects and the impact of any overly influential sites will be investigated by assessing the cluster-bootstrap stability of the analysis. Resampling analysis will be conducted stratified by person and site. The analysis will be conducted within each replication and the variability will be assessed in terms of statistical significance, clinically meaningful effect size, and the distribution of observed treatment effects. Any deviations impacting performance will be mitigated by modification of the primary analysis potentially to an approach utilizing the Huber-White sandwich estimator for the variance.

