Analysis of Secondary Measures: The analysis of all secondary outcome measures will use similar hierarchical generalized linear models to those described in the primary analysis above. Analyses of all secondary measures enhance and further characterize any effect demonstrated by the primary endpoint as opposed to alternative efficacy measures. Therefore no adjustments for multiple comparisons are necessary nor planned.

For continuous outcome measures of CAL and OHIP-5 we will use the same analytical framework described for the primary outcome, consisting of a mixed effects linear model with random effects for site, patient and provider and fixed effects for time (indicators for 6-week, 12 months) and treatment including a treatment by time interaction. Significance of either interaction term will represent a difference between the treatment and control arm at that timepoint, with the 6-week time representing efficacy and the 12-month time representing long-term efficacy/durability. No transformation of these variables is likely to be necessary.

For the secondary binary outcomes of BOP and the presence of residual disease (tooth level), we will use the generalized extension of the HLM using a logit link and binomial family (aka multilevel logistic regression, random coefficients logistic regression). The terms included in the model will be identical to that described for the continuous outcomes above.

The secondary outcome of remission (participant level) differs from the others in that it is measured at the person level and that the model is not longitudinal given that there is no variability at baseline (i.e., all participants at baseline meet the criteria of this outcome as it is part of the inclusion criteria for participation). Thus, outcome will be evaluated using mixed effects logistic regression, with a random effect for provider and a fixed effect for treatment assignment. This will be conducted separately at reevaluation (6 weeks) and final study visit (12 months). A significant and positive term for arm would indicate an effect of the treatment.

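### The protocol does not settle which visit carries the primary test: 5.3 says 12 months, other sections use 6 weeks and 12 months, and 12.4 has two unordered tests at 0.05

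*Protocol*

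**What the plan says.** **Primary timepoint.** Protocol section 5.3, in justifying the attrition allowance, says: "Because the primary endpoint occurs 12 months following treatment". Section 3.1 describes the primary outcome as "full-mouth probing depth (PD) at 6 weeks to 12 months post-intervention adjusted for baseline PD". The primary objective in the Protocol Summary names both visits, and section 12.2 introduces the primary outcome as PD change at each timepoint.

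**Test.** Section 12.4 (Primary Outcome Analysis) announces a test of one primary hypothesis. The model uses "two dummy indicators representing re-evaluation at 6 weeks and final study visit at 12 months", an arm indicator and their interactions. It then states: "Significance of either interaction term will represent a difference between the treatment and control arm at that timepoint". The rest of that sentence gives the two visits different labels: "with the 6-week time representing efficacy and the 12-month time representing long-term efficacy/durability".

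**Alpha.** Section 12.4 (Analysis Population): "All statistical tests will be evaluated using a two-tailed alpha level of .05".

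**Multiplicity.** The only statement is in the paragraph on secondary measures: "Therefore no adjustments for multiple comparisons are necessary nor planned". It is argued from the supporting role of those measures and does not address the two primary terms.

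**Sample size.** Section 12.2 simulates a mean change of 0.3 mm on placebo and 0.5 mm on AMXM, analyses the data with the 12.4 model, and reports 90% power at 220 per arm. It names no visit and no success criterion.

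**The concern.** The protocol needs a single verdict on the primary outcome but gives no rule for reaching one when the two visits disagree. Two provisions depend on that verdict. The missing-data text in 12.4 runs tipping-point analyses only if the study is positive. The waiver of multiplicity adjustment for secondary measures rests on an effect shown by the primary endpoint, in the singular. Neither can be applied to a split result, such as 6 weeks significant and 12 months not.

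The split matters clinically. A difference that has gone by 12 months and one that persists support different guidance on antibiotic use, which is what this trial is meant to inform. If the choice of visit is left until results are known, it can follow the results, and the error rate of the primary claim is no longer the stated 5%.

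**Working it through.** **Inputs from the protocol.** Two arm-by-time terms, each at two-sided 0.05 (critical value c = 1.96); shared baseline and random intercepts (12.4); 220 evaluable per arm, 0.2 mm difference, 90% power, 20% dropout (12.2).

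**Assumed input.** The protocol does not give the correlation r between the two test statistics. Under a random-intercept structure with residual variance s², each change from baseline has variance 2s² and the two changes have covariance s² (the shared baseline), so r = s²/(2s²) = 0.5. The range 0 to 0.9 is shown because the real structure may differ.

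**The plan's own figure.** 220/(1 − 0.20) = 275 per arm, or 550. The plan states 544 = 34 × 16, or 272 per arm, within about 1% of 550. The dropout step therefore reproduces. The 220 itself comes from a simulation whose correlations are not stated, so it cannot be checked in closed form.

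**Error rates if either term counts.**

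- Two-sided familywise error = 1 − P(|Z1| < 1.96 and |Z2| < 1.96)
- False claim favouring AMXM = 1 − P(Z1 < 1.96 and Z2 < 1.96)

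with (Z1, Z2) standard bivariate normal with correlation r:

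| r | Two-sided | Favouring AMXM |
|---|---|---|
| 0 | 9.75% | 4.9% |
| 0.3 | 9.5% | 4.8% |
| 0.5 | 9.1% | 4.5% |
| 0.7 | 8.35% | 4.2% |
| 0.8 | 7.8% | 3.9% |
| 0.9 | 7.0% | 3.5% |

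At r = 0 the two-sided value is 1 − 0.95² = 9.75%. Simulating person-level changes from baseline (220 per arm, 10,000 runs) under random intercepts gave 9.1% and 9.35% for intraclass correlations of 0.3 and 0.6.

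**If 12 months alone is primary.** One test: 5% two-sided, 2.5% favouring AMXM.

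**Power, depending on what the simulation counted.** Suppose the 90% was the chance that at least one term is significant, with the same true effect at both visits. Solve 1 − P(|Z1 + d| < 1.96 and |Z2 + d| < 1.96) = 0.90 for the standardised effect d, then take the power of one term alone. At r = 0.5, d = 2.73 and single-term power is 78%. It is 68% at r = 0 and 86% at r = 0.9. If the 90% was for one term, 12-month power is 90% as stated, provided that term is the 12-month one or the simulated effect applies at that visit.

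**Cost of an alpha split, if the 90% refers to one term.** The implied person-level SD is 0.2 × √(220/2)/(1.960 + 1.282) = 0.647 mm. At 0.025 per visit:

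- power at 220 per arm is Φ(3.24 − 2.24) = 84%
- 90% power needs 2 × 0.647² × (2.241 + 1.282)²/0.2² = 260 evaluable per arm, or 260/0.8 = 325 randomised per arm
- familywise error is 4.65% at r = 0.5.

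**The case against.** The best defence is that 12.4 ties each significant term to its own visit and labels the visits differently, so it makes two separate claims, each at 5%, and never says that either one makes the trial positive. On that reading, a result at 6 weeks only would be reported as efficacy without durability. This stands as far as it goes: a reader might infer that the protocol declares success on either term, and it does not say so. But both terms are offered as the test of one hypothesis, and two later provisions need one verdict that the text does not supply.

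A reader might also infer that the primary error rate is simply 8–9%. That is not established. Under 5.3 alone it is 5%, and under the either-term reading the figure depends on a correlation that the protocol does not give.

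Nor do the documents support saying that a false call for antibiotics exceeds 5%. The two-sided figures include false findings against AMXM. In favour of AMXM the rate stays below 5% at every correlation shown. The relevant comparison is with 2.5%.

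It is tempting to add that the sample size covers one contrast and so needs no change. Section 12.2 does not say which term, or whether either term, counted as success.

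Finally, a testing order is often left to the SAP, which is not shown here. The absence of one would not be a finding by itself. The conflict over the primary timepoint is in the protocol's own text.

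**Conclusion.** The point holds as an inconsistency with a conditional effect on error. The protocol names 12 months in one place and both visits elsewhere, and it tests one hypothesis with two unordered terms at full alpha.

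Under the either-term reading, two-sided error is about 9% and the chance of a false claim favouring AMXM is nearly double the nominal 2.5%. Under the 12-month reading there is no inflation. These rates assume valid standard errors from the planned model and, for the central values, a correlation of 0.5. The meaning of the stated 90% power is open for the same reason. The matter should be settled before unblinding.

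**What to change.** 1. In 3.1, 12.1, 12.2 and 12.4, and in the Protocol Summary, state one primary contrast: the 12-month arm-by-time term at two-sided 0.05. This is consistent with 5.3.
2. Test the 6-week term at two-sided 0.05 only if the 12-month term is significant. Otherwise report it with its confidence interval as descriptive. Another pre-specified order or an alpha split would also control the error.
3. In 12.2, state which term the 90% power at 220 per arm refers to. If the simulation counted either term as success, restate the power for the 12-month term.
4. In the missing-data section, define a positive study by the same contrast.

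The cost is a few sentences. The fixed sequence uses full alpha at 12 months, so it needs no larger sample if the stated power already refers to that term. If it does not, the restated power will show whether 272 per arm is still enough.

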To address limitations in evidence pertaining to adjunctive antibiotic use as part of NSPT, the study objective is to assess the effectiveness of systemic AMXM combination antibiotics as an adjunct to SRP (AMXM group) vs. SRP alone (Placebo group) in periodontal patients with Stages II-III, Grade A-C periodontitis who receive care in clinical practices within the National Dental PBRN. In brief, patient participants in

the AMXM group will receive a loading dose of Amoxicillin 500mg and Metronidazole 500mg followed by a self-administered dose (500mg) of the two drugs every 8 hours (qh8) for 10 days. This regimen was employed in a recent periodontitis clinical trial of forty-two adult patient participants and demonstrated a high safety profile with no drug-related adverse events (Ramón Gómez-Sandoval et al. 2020). Additionally, the present study will include effect modification analyses for sample subpopulations of interest, such as smokers versus non-smokers and groups with different rates of disease progression from more chronic (Grade A) to more aggressive (Grade C), in order to assess whether there may be benefit to adjunctive antibiotics targeted to specific populations.

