For participating practitioners, we will collect information from the practitioner database on practitioner demographics (age, gender, race-ethnicity), primary practice setting (e.g., solo private practice, group practice, managed care, academic, public health, etc.) and location (region, state, zip code), practice type (general dentist, specialist, and dental hygienist), specialty training, year of dental school graduation, and frequency of NSPT performed. We also will collect available practitioner-reported percentages of patients by age group, race-ethnicity, and dental insurance type. Practitioners will be asked to review and update, if necessary, their practice information as part of becoming research ready.

Each participating practitioner is assigned a practitioner identification number (PID) in the database, which will be used to register practitioners in the study. The PID will then enable linkage to each practitioner's demographic and practice data for analysis.

Patient participants

Participant data recorded by the practitioner / office staff: medical/medication history and clinical data will be captured on eCRFs and through a periodontal software application, which will be screen shot and uploaded to the EDC, to include:

- Medical history: medical history at baseline appointment, to include allergies to antibiotics and anesthetics. Subsequent study visits- review and report any new issues as part of AE process. Counsel patient participants on the need for secondary forms of birth control for females, and the possibility of GI distress, fungal and/or yeast infections based on antibiotics used in the study. Current cigarette smoking and confirmation via self-report of last known HbA1c score at or above 10%, harmonized to groupings used by the AAP (Tonetti et al. 2018).
- Medication history: listing of current medications, both prescription and over the counter; recent antibiotic use, history of allergy to antibiotics. Only changes to medications related to AEs will be tracked and reported after the Baseline visit. Discuss prohibited medications based on known contraindications (e.g., Lithium, as well as substances such as alcohol). In case the patient participant is unaware of their complete list of medications at screening they will need to provide that at the baseline visit.
- Evaluate and assign ASA classification based on current guidelines at baseline.
- Periodontal assessment will be recorded at all study visits:

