Key Subgroup Analyses & Analyses by Sex, Race and Ethnicity: In order to determine whether any key differences exist by age, sex, or race and ethnicity, analyses of each outcome will be conducted to assess if differences in the intervention effect are to be expected. For our regression analyses, this will take the form of the addition of an interaction term between treatment and subgroup, with a significant p-value suggesting a statistically meaningful difference between the effects experienced by the subgroups. Any significant differences will be examined to determine whether they are of a clinically significant magnitude and comparison of intervention effects will be achieved by reporting intervention effects and their confidence intervals separately for each sex and

for each race/ethnicity group. Further, the raw data will be summarized using boxplots (continuous) or bar charts (binary), stratified by subgroup to visually represent key differences should any be found. These analyses are supported by our randomization scheme which should result in relative balance of treatment assignment across subgroups resulting in unbiased effect estimates.

We will also perform secondary evaluations of the primary outcome measure to assess whether there is effect modification based on age and periodontitis stage and grade, which are key variables associates with periodontitis.

The analysis will consider the following variables:

- Race/ethnicity: non-Hispanic White, non-Hispanic Black, Mexican American, Other Hispanic, Other Race
- Age: continuous variable
- Sex: male or female
- Periodontitis Stage: II, III
- Periodontitis Grade: A, B, C

To test these potential moderators, we will adapt the model described for the primary outcome to include the moderator and product of the moderator and arm in the third level of the model for predicting all level 1 terms. A significant omnibus test based on a contrast would provide support for effect modification. We will probe the nature of any significant interaction by examining the pairwise differences in differences of the change (i.e., moderator X arm X time) and by plotting these values to facilitate interpretation.

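### Section 12.4 omits the smoker comparison announced in 2.2, and for age, sex and race/ethnicity on the longitudinal secondary outcomes it names only a two-way interaction that averages in the baseline visit

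*Protocol*

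**What the plan says.** **Smoking.** Protocol 2.2 says the study will include "effect modification analyses for sample subpopulations of interest, such as smokers versus non-smokers and groups with different rates of disease progression", running from Grade A to Grade C. Section 8.1 lists among the recorded data "Current cigarette smoking and confirmation via self-report of last known HbA1c score", and 7.1 takes a tobacco use history. In 12.4 the text on the primary outcome names "effect modification based on age and periodontitis stage and grade". The list of variables below it has race/ethnicity, age, sex, stage and grade, and no smoking.

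**Form of the interaction.** For age, sex and race/ethnicity, 12.4 says that "analyses of each outcome will be conducted to assess if differences in the intervention effect are to be expected", and that for the regression models "this will take the form of the addition of an interaction term between treatment and subgroup". A significant p-value is then read as a difference in effects between subgroups.

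**The models these terms enter.** In 12.4 the primary model has indicators for 6 weeks and 12 months, an arm indicator, and arm-by-time interactions. The interactions are the treatment comparison at each visit. CAL and OHIP-5 use the same framework, and BoP and residual disease use the same terms on the logit scale. Remission is modelled separately at each follow-up visit, and there the arm term is the treatment effect.

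**Moderators of PD.** Later in the same subsection the PD model is extended so that the moderator and its product with arm predict every level 1 term. Any significant result is probed as moderator by arm by time. The variable list for this model includes race/ethnicity, age and sex.

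**The concern.** Smoking is the first example of an effect modifier in the rationale and is missing from the analysis section. If a smoker analysis is reported later, a reader could not tell whether it was planned: 2.2 says yes, and the list in 12.4 says no.

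The interaction form raises a different problem. With baseline in the outcome vector, the arm main effect is the baseline difference between arms, which randomisation makes zero in expectation. The treatment effect sits in the arm-by-time terms. To ask whether it differs by subgroup, the subgroup must interact with those terms. A lone arm-by-subgroup term instead mixes a pre-treatment visit, where no effect can exist, with the two follow-ups. At stake are shrunken estimates of effect modification on four secondary outcomes, and p-values that partly reflect chance baseline imbalance.

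**Working it through.** **1. The plan's own sample size.** Inflating 220 per arm for 20% dropout gives 220/0.80 = 275 per arm (550). The protocol states 272 per arm, 544 = 34 × 16, which agrees within about 1%. The 220 comes from a custom simulation whose site correlations are not given. Taking 1 mm as a participant-level SD gives 2(1.96 + 1.282)² × 1²/0.2² ≈ 526 per arm. So 220 per arm implies a participant-level SD of change of 0.2/(3.242 × √(2/220)) = 0.647 mm. No subgroup power is stated.

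**2. What the two-way term estimates.** Let the subgroup difference in the arm contrast be 0 at baseline, d₆ at 6 weeks and d₁₂ at 12 months. In a linear random-intercept model with complete data, an arm-by-subgroup term without the three-way terms estimates (0 + d₆ + d₁₂)/3.

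| True d₆, d₁₂ (mm) | Two-way, expected | Two-way, simulated |
|---|---|---|
| 0.2, 0.2 | 0.133 | 0.135 |
| 0.2, 0 | 0.067 | 0.064 |
| 0, 0.2 | 0.067 | 0.063 |
| 0.2, −0.2 | 0 | 0.000 |

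The simulated column is a large-sample check at an assumed correlation of 0.5. Sixty mixed-model fits of the first case at 440 participants averaged 0.134 (Monte Carlo SE 0.013). When the three-way terms are included they recover about 0.20 at each affected visit, and the arm-by-subgroup coefficient falls to about zero (within 0.01), because it is then only the baseline difference.

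**3. Power.** Assumptions: 440 completers, 110 in each of the four arm-by-subgroup cells; equal variances and equal correlation ρ between visits; d = 0.2 mm at both follow-ups; two-sided 0.05. The variance at one visit is s² = 0.647²/[2(1 − ρ)]. SE = √(V × 4/110), and power ≈ Φ(effect/SE − 1.96).

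- Two-way: effect 0.133, V = s²(1 + 2ρ)/3. At ρ = 0.3, s² = 0.299, V = 0.160 and SE = 0.076, so power is 42%. At ρ = 0.5, 0.7, 0.8 and 0.9 it is 26%, 15%, 11% and 7%.
- Three-way, one visit: effect 0.2, V = 0.647², SE = 0.123. Power is 37% at any ρ.
- Three-way, average of both follow-ups against baseline: V = 1.5s²(1 − ρ) = 0.75 × 0.647², SE = 0.107. Power is 46.5% at any ρ.

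The two-way term beats the one-visit test when (4/9) × 6(1 − ρ)/(1 + 2ρ) > 1, that is when ρ < 5/14 ≈ 0.36.

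**4. Smoking, side by side.** Section 2.2 names smoking and disease progression (grade) as two comparisons. Section 12.4 carries grade forward and not smoking. Section 4.2 mentions smoking status among the patient characteristics used in assessing periodontal status under the classification guidelines. Grade may therefore partly reflect smoking, but it does not give a smoker against non-smoker contrast.

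**The case against.** The wording may be shorthand. Section 12.4 states its aim as differences in the intervention effect, and a phrase about treatment and subgroup could cover an interaction with whatever term carries that effect. Exact coding for secondary outcomes is often left to a statistical analysis plan, which the protocol lists as a supplement. This tempers the point but does not remove it. The same subsection spells out the three-way form when it means it, and does so only for PD.

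The outcome tables in Section 3 speak of adjusting for baseline values. If baseline were a covariate only, the two-way term would average the two follow-ups, and a constant difference would be undiluted: (d + d)/2 = d. But two visit indicators alongside an arm term need a third visit as reference. Section 12.4 also explains that remission is not longitudinal because it does not vary at baseline.

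A reader might infer more than the documents support:

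- *That the two-way rule is wrong for every outcome.* Remission is cross-sectional, so arm-by-subgroup is the right term. PD already has the three-way model for the same variables, alongside the two-way sentence.
- *That the two-way term has nothing to do with the treatment effect.* It is a diluted average of the effect difference.
- *That its power is always much worse.* A contrast such as expected z of 1.6 against 3.5 comes from assuming a person SD of 0.6 and a residual SD of 0.3, a correlation of 0.36/0.45 = 0.8. Below about 0.36 the ranking against a one-visit test reverses.
- *That finding responsive patients is the trial's main aim.* The primary objective is the overall comparison. Effect modification is additional.

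On smoking, the words before the example in 2.2 mark it as an illustration. It is still introduced as something the study will include.

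**Conclusion.** Both parts hold, within limits. Sections 2.2 and 12.4 disagree on smoking. For CAL, BoP, residual disease and OHIP-5, the only stated test of modification by age, sex or race/ethnicity does not match the treatment effect that the protocol itself defines. For PD two forms stand in one subsection, and the moderator-by-arm-by-time form should govern.

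The dilution (2d/3, d/3, or cancellation) follows from the model in 12.4, given complete data and a linear scale. For the two logit models it is approximate, on the log-odds scale. The power figures are an illustration on the PD scale, using the SD implied by 220 per arm, equal-sized subgroups and assumed correlations. The protocol gives no SD for the secondary outcomes and no visit-to-visit correlation. No primary result is affected. The point should be corrected because the rationale presents effect modification as a way to target antibiotic use.

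**What to change.** Add baseline smoking status, in the categories actually collected, to the moderator list in 12.4.

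Replace the two-way sentence with a rule by type of model. For every longitudinal outcome (PD, CAL, BoP, residual disease, OHIP-5), effect modification is tested by the subgroup-by-arm-by-visit terms at 6 weeks and 12 months, with the baseline arm-by-subgroup term left out of the test. For remission, the subgroup-by-arm term in each visit's model is kept. For PD, state that this rule governs and that the omnibus contrast covers the two follow-up terms only, since the moderator product is also set to predict the intercept.

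The cost is one list item and one or two sentences. No new data are needed and the sample size does not change.
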